### **13.3 Record Retention**

The Principal Investigator will maintain adequate records so that the conduct of the study can be fully documented and monitored. Copies of protocols, test result originals, all IP accountability records, correspondence, subject Informed Consent forms, and any other documents relevant to the conduct of the study will be kept on file by the Principal Investigator. Study documents will not be destroyed. For regulatory inspections, it will be necessary to have access to complete study subject records, provided that subject confidentiality is maintained.

Per the Clinical Development Agreement between ParaPRO LLC and Concentrics Research, investigators must retain subjects' records for a period of 2 years after FDA approval or until written approval to destroy the documentation is provided by ParaPRO LLC. The documentation must be retained longer if so required by local law. Investigators must notify Concentrics Research and ParaPRO LLC, in writing, of changes in address, sales of practices or site closures in order to make arrangements for the maintenance of study files.

## **14 FINAL REPORT/PUBLICATION STATEMENT**

Any formal presentation or publication of data collected as a direct or indirect result of this trial will be considered as a joint publication by the investigator(s) and ParaPRO LLC.

Individual investigators may publish data arising from their own subjects with permission from ParaPRO. The Principal Investigator will provide ParaPRO LLC with copies of written publications (including abstracts and posters) at least 60 days in advance of submission. This review is to permit ParaPRO LLC to review the communication for accuracy (thus avoiding potential discrepancies with submissions to regulatory authorities), to verify that confidential information is not inadvertently divulged (including patent protection), to allow adequate input or supplementary information that may not have been available to the Principal Investigator, and to allow establishment of co-authorship.

Data will be reviewed by all participating investigators prior to publication. ParaPRO LLC will have 60 days to review all definitive publications, such as manuscripts and book chapters, and a minimum of 30 days to review all abstracts.

## 16 APPENDIX [1]: EXAMPLE OPEN-LABEL PRODUCT LABEL

### DIRECTIONS FOR USE

See package insert, including the patient information section, for full prescribing and dosing information.

### SHAKE WELL BEFORE USE.

### WARNINGS:

- Keep out of the reach of children.
- Natroba should be used on children under direct supervision of an adult.
- Do not swallow.
- Avoid contact with eyes. If Natroba gets into the eyes, immediately flush with water.
- If scalp irritation or infection occurs after use contact a physician.

Manufactured for:  
ParaPRO LLC, [name]  
Distributed by:  
ParaPRO and/or Perrin Therapeutics Inc.  
Magnolia, TX 77354

### ParaPRO

Natroba and ParaPRO are registered trademarks of ParaPRO LLC.

Natroba contains 9 mg spinosad per gram of compound consisting of Water, Isopropyl Alcohol, Benzyl Alcohol, Hexylene Glycol, Propylene Glycol, Cetearyl Alcohol, Stearalkonium Chloride, Cetareth-20, Hydroxyethyl Cellulose, Butylated Hydroxytoluene, F&DC Yellow #6.

Store at 25°C (77°F); excursions permitted to 15° to 30°C (59° to 86°F).

NDC 52246-929-04

120 mL

Rx only

  
**Natroba™**  
(spinosad)  
Topical Suspension  
0.9%

For topical use

XX

Protocol: SPN-304-15

INVESTIGATIONAL PRODUCT FOR THE TREATMENT OF SCABIES

Site # \_\_\_\_\_ / Screen # \_\_\_\_\_ / Subject Initials: \_\_\_\_\_

Date Dispensed: \_\_\_\_\_

Caution – New Drug: Limited by Federal (U.S.) Law to  
Investigational Use

## LIST OF ABBREVIATIONS AND ACRONYMS

TERM	DEFINITION
AE	Adverse Event
ANCOVA	Analysis of Covariance
ATC	Anatomical Therapeutic Chemistry
CI	Confidence Interval
CMH	Cochran-Mantel-Haenszel (general association test)
ET	Early Termination
FDA	Food and Drug Administration
IP	Investigational Product
ITT	Intent-to-Treat
I-ITT	Index Intent-to-Treat
I-PP	Index Per Protocol
LOCF	Last Observation Carried Forward
MedDRA	Medical Dictionary for Drug Regulatory Affairs
OC	Observed Cases
PI	Principal Investigator
POC	Proof of Concept (study)
PT	Preferred Term
SAE	Serious Adverse Event
SAP	Statistical Analysis Plan
SD	Standard Deviation
SOC	System Organ Class
TEAE	Treatment-Emergent Adverse Event
WHO-DD	WHO-Drug Dictionary

## 1. PREFACE

This document presents a statistical analysis plan (SAP) for ParaPRO Protocol SPN-304-15 (*A Phase 3, Randomized, Double Blind, Placebo-Controlled Study to Assess the Safety and Efficacy of Natroba™ (spinosad) for the Treatment of Scabies*).

Reference materials for this statistical plan include the protocol SPN-304-15 (Amendment 5 Dated: 20 September 2017).

The SAP described hereafter is an *a priori* plan. A version of the SAP will be prepared at the same time as the protocol is finalized. However, the primary and secondary efficacy endpoints and analyses on them will not be altered unless agreed upon with the Food and Drug Administration (FDA). SAP will be finalized before the database is unblinded.

Statistical programming may occur as study data accumulate in order to have analysis programs ready at the time the study finishes. In such an event, arbitrary treatment group assignments must be randomly linked to subjects, effectively rendering any inference based upon the output of programs meaningless.

For the reasons stated here the conduct of the study in the field is considered to be independent of any study outcome that might materialize upon enactment of the currently proposed statistical plan. Any deviations from the statistical analysis plan will be described in the clinical study report.

## 2. PROTOCOL OVERVIEW

### 2.1. Study Objectives

#### 2.1.1. Primary Objective

The primary objective is to assess the safety and efficacy of topical Natroba™ (spinosad) versus Placebo for the complete cure of scabies after a single treatment.

### 2.2. Trial Design and Visit Structure

The primary study is a double blind, two-arm, 28-day, placebo-controlled study enrolling approximately 120 infested “index” subjects enrolled and randomized 1:1 to Natroba™ or Placebo in order to achieve, with attrition, 96 subjects completed in the study.

All members of a household (no more than 6 individuals) with a suspected “index” subject must be screened at the first visit. In this study, “index” subjects are defined as the youngest infested household member ( $\geq 4$  years). If the household has at least one member with active scabies infestation and meet all other criteria, they must all agree to participate in the study. Household members who do not present with scabies at the screening visit must also agree to apply the same blinded investigational product (IP) as household members who present with scabies (see Table 6-1 Schedule of Procedures in the protocol

for status assessment). All household members must agree to participate in the study or none will be enrolled.

After screening on Day 1, all randomized subjects will be dispensed IP (Natroba™ or Placebo) to apply at home later the same day. IP will be applied as a single treatment over the entire body from the neck down to the toes (including the soles of the feet) and to the scalp (if balding) or hairline, temples and forehead on the same day. Subjects less than 12 years of age should be assisted with administration by a parent, guardian or caregiver. Subjects will rub the treatment into the skin followed by a 10-minute wait period before getting dressed. Showering or bathing must not occur earlier than 6 hours after treatment and no later than at least 1 hour prior to Day 2 visit.

On Day 2 (Visit 2), all household members will return for general skin and eye assessments of possible irritation, and to confirm that all IP was left on for a minimum of 6 hours before bathing or showering. If a subject reports an adverse event assessed as related by the principal investigator (PI) on Day 2 (Visit 2) then a follow-up visit with the investigator must be scheduled within 7 days of visit. All household members will receive a well-being phone call on Day 14 to continue to emphasize instructions to prevent re-infestation, determine if any concomitant medications have been used, and check for adverse events

In the randomized population (all household members), on Day 2 (Visit 2), general skin and eye assessments will be made for possible irritation, and to confirm that all IP was left on for a minimum of 6 hours before bathing or showering. Subjects will receive a well-being phone call on Day 14 to continue to emphasize instructions to prevent re-infestation, determine if any concomitant medications have been used, and check for adverse events. If a subject reports an adverse event assessed as related by the PI on Day 2 (Visit 2) then a follow-up visit with the investigator must be scheduled within 7 days of visit. If a subject reports an adverse event assessed as related by the PI on the Day 14 well-being phone call, then a follow-up visit with the investigator must be scheduled within 7 days of the phone call.

On Day 28 (Visit 3), primary population subjects will return to the clinic for safety and efficacy assessments. The primary endpoint of complete cure as well as the key secondary endpoint to determine improvement based on lesion count will be assessed in the “index” subject and any infested household members. If the infested subject is completely cured at Day 28, he or she will have completed the study and termination procedures will be conducted. If the subject is not completely cured at Day 28 (with Natroba™ or Placebo), the subject will receive 5% Permethrin and will be directed to their primary care physician for follow-up.

Safety assessments will be made for all household members and will include monitoring of adverse events (AEs) throughout the study, vital signs recording (Days 1 and 28), and general skin and eye irritation assessments (Days 1, 2, and 28).

The Day 28 procedures will also be completed for early termination (ET) except subjects will not receive rescue Permethrin but will be directed to follow-up with their primary care physician.

## 2.3. Study Treatment

### 2.3.1. Treatment Groups

Subjects will receive one of two treatments randomized 1:1 to the placebo or investigational product.

Treatments:

1	Investigational product: Natroba™ (spinosad) Topical Suspension (0.9%)
2	Placebo: Placebo Control

### 2.3.2. Sample Size Determination

Approximately 120 “index” subjects will be enrolled (includes anticipated 20% attrition) from 120 households and randomized 1:1 to Natroba™ (spinosad) and Placebo control. The index subject will be the youngest infested member of a household ( $\geq 4$  years). Referencing to the Sponsor’s Proof of Concept (POC) study (SPN-401-12) and published literature, it is reasonable to assume a 60% complete cure rate for Natroba™ and 30% for placebo. A sample size of 48 study-completed “index” subjects per group will provide 80% power to declare the non-equivalency using a delta of 30% and Type I error rate of 0.05. Fisher exact test was used to calculate the sample size and the specified power in the following Table 1 (PASS 14; 2015, NCCSS, LLC., Kaysville, Utah, USA. [www.ncss.com](http://www.ncss.com)).

**Table 1 Sample Size Needed to Declare Non-equivalency with Respect to the Proportion of Subjects Achieving Complete Cure with a Type I Error Rate=0.05 and Specified Power**

Natroba™	Proportion in		Required Sample Size per Group	Power
	Placebo	Difference vs. Placebo		
55%	30%	25%	69	80.4%
60%	30%	30%	48	80.0%
65%	30%	35%	37	80.6%

Assuming a drop-out rate could be at most 20%, 120 subjects should guarantee at least 48 evaluable subjects for each treatment group at Day 28 assessment.

### **2.3.3. Method of Treatment Assignment and Randomization**

As “index” subjects and other infested or non-infested household members become eligible for randomization at Visit 1 (Day 1), the site will locally assign a unique subject number to each of the qualified household members that combines a 3-digit site number (xxx), a 2-digit household number (yy), and a 2-digit household member number (zz). For example, the first subject of the first household at site 101 would be randomized to subject number 101-01-01, the second member to 101-01-02, the third member to 101-01-03, and so on. Since all household members receive the same treatment, each household is randomized to either Natroba™ (spinosad) or Placebo control. Non-infested household members will be assigned the same IP treatment as the infested members and will be assigned a subject number and randomization number. The assigned subject numbers to each household will correspond to unique bottle numbers on a scheme that unblinded site personnel will assign and distribute, to ensure approximately equal randomization of households to either treatment. Subject numbers must not be re-used once assigned, even if the subject does not take the IP. Randomization will be stratified by study site.

### **2.3.4. Blinding Methods**

Eligible subjects will be assigned to either treatment group, Natroba™ (spinosad) or Placebo control, by pre-specified un-blinded site personnel that may perform no other subject related study specific or subject treatment related study duties. The un-blinded site personnel will assign all members from the same household to the same treatment group. The assigned subject numbers in each household will correspond to unique bottle numbers on a scheme that unblinded site personnel will assign and distribute to ensure approximately equal randomization of households to either treatment. Subjects, blinded site personnel, and ParaPRO, LLC will remain blinded to the treatment until after database lock.

### **2.3.5. Procedures for Unblinding**

In an emergency, the study blind may be broken only if:

- in the opinion of the investigator and/or the Medical Monitor, it is in the subject's best interest to do so;
- knowledge of the treatment will alter the clinical management of the subject;
- approval has been granted by the Medical Monitor and/or ParaPRO, LLC.

Whenever possible, the Medical Monitor should be notified prior to unblinding a treatment assignment. In the event that unblinding is necessary for the medical management of the subject, the pre-specified un-blinded site personnel will access the randomization code by a treatment code list provided by Concentrics Research to each site. If a treatment assignment is unblinded, the date and reason for the unblinding must be recorded on the subject's source document, and the Medical Monitor notified within 24 hours.

## **2.4. Planned Analyses**

The analysis of all study data will occur at the end of the trial. No interim analyses are planned. Study data will remain blinded to treatment assignment until all data have been collected and the clinical database has been locked for unblinding and analysis.

## **3. SAFETY PARAMETERS**

### **3.1. Adverse Event**

Adverse Events (AEs) will be collected on Days 2, 14 (phone call, and a follow-up visit if AE is reported), and 28/ET. See Section 6.4.1 for further details on which AEs will be assigned as treatment-emergent adverse events (TEAEs).

### **3.2. General Skin and Eye Assessments**

On Day 1, the skin will be assessed to determine eligibility – no evidence of crusted scabies, normal skin in non-infested areas. On Days 1 and 2, the skin and eye assessments will include documentation of presence or absence of irritation, and verbal verification that the treatment topical suspension remained on for at least 6 hours before being washed off. On Day 28/ET, skin and eye assessments will include evidence of irritation.

Eye irritation will be rated:

- 0 no irritation
- 1 mild scleral, lid, and/or conjunctiva injection
- 2 moderate scleral and or lid injection with conjunctival erythema
- 3 severe scleral and/or lid injection with conjunctival erythema and purulent drainage

### **3.3. Vital Signs**

Height (Day 1 only), weight, resting blood pressure and heart rate will be measured on Days 1 and 28/ET.

### **3.4. Prior and Concomitant Medications**

For randomized subjects, prior medications will be collected on Day 1 and concomitant medications will be collected on Days 2, 14 (by phone), and 28/ET.

## **4. EFFICACY PARAMETERS**

### **4.1. Scabies Assessment**

Skin will be examined on Days 1 and 28/ET to establish positive or negative evidence of active scabies infestation.

- Scabies diagnosis – active scabies infestation confirmed by clinical signs and symptoms (evidence of burrows or presence of scabies)

inflammatory/non-inflammatory lesions and pruritus) as well as by microscopic exam of skin scraping or dermatoscopy to demonstrate the presence of mites, eggs, and/or scybala. If dermatoscopy is used it should also confirm there are burrows on the skin.

- Primary Efficacy Endpoint – complete cure is defined as demonstration of clinical cure (all signs and symptoms have completely resolved, including burrows, inflammatory/non-inflammatory lesions and pruritus) and microscopic or dermatoscopic cure with demonstration of the absence of mites, eggs, and/or scybala, and dermatoscopy negative for burrows.

Lesions should be indicated on a body diagram and/or marked with skin marker; count of existing and new lesions will be recorded.

## **5. ANALYSIS POPULATIONS**

### **5.1. Safety Population**

The safety population will comprise all study subjects who received one dose of IP. Subjects will be analyzed as treated. The safety population includes the index subjects along with any household members enrolled in the study. Safety analyses will utilize the safety population. It is assumed that approximately 360 subjects will be enrolled and receive one administration of IP: 120 “index” subjects and 240 “non-index” subjects.

### **5.2. Intent-to-Treat Population**

The intent-to-treat (ITT) population will comprise all subjects who were randomized. Subjects will be analyzed as randomized. This population includes the index subjects along with any household members enrolled in the study.

### **5.3. Index Intent-to-Treat Population**

The “index” intent-to-treat (I-ITT) population will comprise of all index subjects who were randomized. Subjects will be analyzed as randomized. The index subject will be the youngest infested member of a household ( $\geq 4$  years). Efficacy analyses will be based on this population.

### **5.4. Index Per Protocol Population**

The “index” Per Protocol (I-PP) population is a subset of the I-ITT population. Index subjects will be excluded from the I-PP population for the following reasons:

1. Protocol deviations that would be in violation with the established Inclusion or Exclusion Criteria.
2. Protocol deviations that could confound the evaluation of efficacy outcomes:
  - Scabies assessment not performed (i.e. burrows, lesions, pruritis, skin scraping).
  - Subject received the wrong treatment.

- Discontinuation prior to acquisition of Visit 3 (Day 28) efficacy measurements.
3. Protocol deviations that are a result of subject non-compliance:
- Missed Day 2 appointment.
  - Use of another scabicide during the study.
  - Use of prescription or OTC medicated lotions during the study.

Prior to database lock, a memo will be generated identifying any subjects that were excluded from the I-PP population along with the reason why they were excluded.

The I-PP population will be established after a review of protocol deviations. This analysis population will be used for sensitivity analyses for the primary efficacy analysis.

## **6. STATISTICAL METHODOLOGY**

### **6.1. Statistical and Analytical Issues**

#### **6.1.1. Statistical Methods**

This statistical analysis plan (SAP) will describe statistical analyses for the study and be completed at the same time as the protocol. Any revisions (both alternative and additional methods) to the SAP, and reasons for such revisions, will be described in the final clinical study report.

Data collected in this study will be presented using summary tables, figures, and subject data listings. Summary tables will present data by treatment group and, if applicable, by time of collection. Continuous variables will be summarized using descriptive statistics, specifically the number of non-missing observations, mean, median, standard deviation, minimum and maximum. Categorical variables will be summarized by frequencies and percentages. Figures may be used to support the presentation of certain data.

All tests of significance, unless otherwise stated, will be performed at a significance level of  $\alpha=0.05$ , two-sided.

Statistical programming and analyses will be performed using SAS® Software (SAS Institute Inc., Cary, NC) Version 9.2 or higher.

All subject study data, including data not appearing in tables or figures, will be presented in data listings.

#### **6.1.2. Computed Variables**

The following variables will be computed programmatically.

Age in years (truncated to an integer value) will be calculated using the formula:

Age = integer part of [(Date of informed consent/assent date – date of birth + 1)/365.25]

Improvement will be graded post-treatment as follows:

Mild = <50% reduction in total number of lesions

Moderate =  $\geq$ 50% in total number of lesions

Good = complete clearance of lesions

Baseline value will be the last measurement obtained prior to first dose.

The total number of lesions post-treatment is calculated using the following formula:

Total post-treatment lesions =  
total number of pre-existing lesions + total number of new lesions

The change from baseline is calculated using the formula:

Change from baseline to post-treatment = Post-treatment Value – Baseline Value

The percent reduction in lesions is calculated using the formula:

Percent Reduction =  
$$\frac{[(\text{Baseline total number of lesions} - \text{Post-treatment total number of lesions}) / (\text{Baseline total number of lesions})] * 100}{}$$

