## 1.2 Rationale

ParaPRO conducted a proof-of-concept trial that was a double-blinded, two-arm 28-day placebo controlled study of subjects randomly assigned 3:1 to Natroba™ or Placebo. Subjects applied a single treatment over the entire body from the neck down to the toes (including the soles of the feet) in-clinic on Day 1, rubbing the investigational product (IP) into the skin and waiting 10 minutes before getting dressed. Showering or bathing was to occur no earlier than 6 hours after treatment. Efficacy assessments included visual skin assessment of scabies infestation (visual assessment of burrows, lesion counts, and presence of new lesions), skin scraping for microscopic examination (for evidence of mites) and a pruritus score by a subjective scale. The scabies scores were changed by -1.4 with Natroba (p=0.0020), compared to -1.0 with Placebo (p=0.2500). The count of lesions was significantly decreased with Natroba (-28.1, p=0.0020), however, not with Placebo (-9.8, p=0.6250). Microscopy showed significant improvement, 13/15 negative with Natroba (p=0.0074), compared to 3/5 with Placebo (p=1.000).

The design for the current Phase 3 trial is similar to the phase 3 trials evaluating efficacy of Natroba™ Topical Suspension for treatment of head lice, although subjects in this trial received only one application of the Natroba™ Topical Suspension. In the two phase 3 studies of individuals with lice, all subjects who were treated on Day 0 returned for efficacy evaluation at Day 7. Subjects with live lice present at Day 7 received a second treatment. Subjects who were lice free on Day 7 were to return on Day 14 for evaluation. Subjects with live lice and who received a second treatment on Day 7 were to return on Days 14 and 21 for evaluation. Efficacy was assessed as the proportion of primary subjects who were free of live lice 14 days after the initial/final treatment.

Based on the safety and efficacy of Natroba™ (spinosad) Topical Suspension, 0.9% in the treatment of head lice, the present study is designed to evaluate pivotal phase 3 data on the safety and efficacy of the topical suspension against scabies, an infestation by *Sarcoptes scabiei var. hominis*. The effect of the Natroba™ (spinosad) Topical Suspension, 0.9% will be compared to that of a Placebo control.

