## 8.4 Missing Values

There will be no imputation for missing events and assessments in handling safety data.

If a subject has observed data for complete cure at Day 28, the observed cases (OC) will be used at Day 28. If a subject discontinues the study before Day 28, the imputation method for complete cure at Day 28 depends on the reasons of missing, i.e. informative or non-informative missing. Please refer to the SAP for more details.

For other missing efficacy data at Day 28 (e.g., clinical cure, microscopic cure, new lesions and total lesions), Last Observation Carried Forward (LOCF) imputation will be used.

Details of imputation rules for efficacy analyses and other missing data handling conventions will be included in the SAP.

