#### Total Lesion Counts

Total lesion counts will be calculated as the sum of pre-existing lesions and new lesions. The baseline captures the total lesions on the day of first study drug administration.

The change from baseline to Day 28 will be analyzed using an analysis of covariance (ANCOVA) model with treatment and study site (small sites pooled) as factors and baseline total lesion counts as a covariate.

This analysis will be performed on the I-ITT population using LOCF approach. In addition, descriptive statistics will be provided by visit based on OC data.

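### Read literally, the SAP's lesion grade codes unchanged or higher lesion counts as Mild improvement; separately, a lesion endpoint called key secondary in the design text is only exploratory in the analysis sections.

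*SAP*

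**What the plan says.** **The grade.** SAP 6.1.2 lists variables to be derived by program, among them a post-treatment improvement grade. The lowest level is "Mild = <50% reduction in total number of lesions". The middle level is 50% or more, with no upper limit. The top level is "Good = complete clearance of lesions". The same section defines the post-treatment total as "total number of pre-existing lesions + total number of new lesions". Percent reduction is baseline minus post-treatment total, divided by baseline, times 100. No level covers no change or worsening.

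**Where the grade goes.** No analysis section of either document mentions it again. SAP 6.1.1 says in general terms that categorical variables are summarized by frequency and percentage and that all subject data are listed.

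**The endpoint's status.** The Day 28 paragraphs of Protocol 3.1 and SAP 2.2 refer to a key secondary endpoint that determines improvement from lesion count. The matching synopsis paragraph names only complete cure. Protocol 8.5.3 and SAP 6.3 contain primary and exploratory headings only, and new lesions and total lesion counts sit under the exploratory one. Protocol 8.5 and SAP section 1 both say that primary and secondary efficacy endpoints will not be altered without FDA agreement.

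**The concern.** A scale headed improvement should not return a grade of improvement for someone who has not improved. Here the lowest grade has only an upper limit, and the quantity being graded can fall below zero. Because the variable is to be programmed, the programmer must either follow the rule as written or invent an unwritten one.

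The second matter is the standing of a lesion result. The design text calls a lesion endpoint key secondary, and two passages protect secondary endpoints from change, yet none is defined. A reader cannot tell which lesion variable, if any, the FDA commitment covers, or whether a favorable lesion result could be presented as a key secondary finding.

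**Working it through.** There is no planned figure to reproduce, because neither document gives a number for the grade. The check is to apply the rule as written and then compare the sections on endpoint status.

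**1. The rule.** Inputs, all from SAP 6.1.2:
- Post-treatment total P = pre-existing lesions + new lesions.
- Percent reduction R = (B − P) / B × 100, where B is the baseline count.
- Mild if R < 50; Moderate if R ≥ 50; Good if P = 0.

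The documents give no individual counts, so B = 20 is an assumption. The sign of R does not depend on that choice for any B above zero.

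| Post-treatment total P | R | Grade as written |
|---|---|---|
| 0 | (20 − 0)/20 = 100% | Moderate and Good |
| 5 | (20 − 5)/20 = 75% | Moderate |
| 10 | (20 − 10)/20 = 50% | Moderate |
| 11 | (20 − 11)/20 = 45% | Mild |
| 19 | (20 − 19)/20 = 5% | Mild |
| 20 | (20 − 20)/20 = 0% | Mild |
| 25 | (20 − 25)/20 = −25% | Mild |
| 40 | (20 − 40)/20 = −100% | Mild |

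The last three rows are the defect: an unchanged count, a rise of a quarter and a doubling all receive the grade given to a 45% reduction. The first row shows the overlap at the top.

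**2. The other reading.** If the word reduction is taken to require R > 0, the last three rows drop out of Mild. No other grade takes them, so those subjects are unclassified, and the SAP does not say how they would be shown or whether they stay in a denominator.

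**3. Reach.** The primary analysis is a CMH test on complete cure. Total lesions are analyzed by ANCOVA on the change in count, and new lesions by negative binomial regression. None of these uses the grade. It can reach a report only through a listing or a frequency table made under the general text of SAP 6.1.1.

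**4. Endpoint status side by side.**

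| Place | Status of lesion endpoint |
|---|---|
| Protocol synopsis, Day 28 paragraph | not mentioned |
| Protocol 3.1 | key secondary |
| SAP 2.2 | key secondary |
| Protocol 8.5.3.2 | exploratory |
| SAP 6.3.2 | exploratory |
| Protocol 8.5 and SAP section 1 | secondary endpoints protected, none named |

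The design text and the analysis text cannot both be right.

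**The case against.** The best defense is that nothing depends on the grade. No test uses it and no table of it is specified. The scale is headed improvement, so leaving non-improvers ungraded is workable, and most readers would code complete clearance as Good. On status, the analysis sections of both documents agree on exploratory, and the synopsis names only the primary endpoint. This stands as a limit on importance. It does not repair the rule: the SAP does not state that non-improvers are ungraded, and the literal code says otherwise.

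Three stronger readings are tempting, and the documents do not support them.

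*That dropouts would be counted as mildly improved.* Protocol 8.4 says that for "new lesions and total lesions), Last Observation Carried Forward (LOCF) imputation will be used", and SAP 4.1 says "Skin will be examined on Days 1 and 28/ET to establish positive or negative evidence of active scabies infestation". A reader might infer that a dropout carries baseline forward, giving R = 0% and Mild. With "Assuming a drop-out rate could be at most 20%, 120 subjects should guarantee at least 48 evaluable subjects for each treatment group", that suggests up to 60 − 48 = 12 of 60 per arm (20%). But in SAP 6.3.2 the sentence "This analysis will be performed on the I-ITT population using LOCF approach" refers to the ANCOVA, and the next sentence bases descriptive lesion statistics on observed cases. The Protocol 8.4 list, which is by way of example, does not name the grade. The grade is defined on a post-treatment count, which a carried-forward baseline is not. Protocol 6.7 also asks for all Visit 3 procedures at early termination. The 12 is simply the attrition ceiling and does not measure this defect.

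*That the proof-of-concept trial shows counts rising on placebo.* Protocol 1.2 reports: "The count of lesions was significantly decreased with Natroba (-28.1, p=0.0020), however, not with Placebo (-9.8, p=0.6250". With an exact paired sign or signed-rank test, changes all in one direction give p = 2/2^m for m non-zero changes (1, 0.5, 0.25, 0.125, ...), never 0.625, so at least one increase would follow. But the test is not named. An unpaired comparison of 5 baseline and 5 final counts with an assumed SD of 30 gives t = 9.8 / (30 × √(2/5)) = 0.52 on 8 df, p about 0.62, with no increase needed. A paired exact test is the more plausible, but the data are on file with the sponsor, and one subject in another trial would not size the problem here.

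*That the three-level grade is the key secondary endpoint.* The wording is close, but neither document links them.

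**Conclusion.** The concern holds as a minor defect of definition and consistency. As written, the grade labels unchanged or worse subjects as mildly improved; on the more charitable reading it leaves them without a grade. This follows from the SAP's own formula and needs no assumption about the data. The conflict over endpoint status is equally plain from the text.

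The effect is limited to listings or any summary of the grade, and to how a lesion result may be described. It cannot be quantified, because the documents give no expected share of non-improvers and plan no table of the grade. Neither the attrition ceiling nor the proof-of-concept p-value should be offered as a measure of size. The primary conclusion of the trial is not touched.

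**What to change.** **Grade (SAP 6.1.2).** Use mutually exclusive levels:
- None/worse: reduction of 0% or less
- Mild: more than 0% and under 50%
- Moderate: at least 50% and under 100%
- Good: 100%

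Apply them to observed post-treatment counts, in line with the observed-case rule that SAP 6.3.2 already sets for descriptive lesion statistics. If the grade will not be reported, delete it.

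**Endpoint status, before unblinding.** Either call the lesion endpoints exploratory throughout, amending Protocol 3.1 and SAP 2.2 and aligning the primary-and-secondary wording in Protocol 8.5 and SAP section 1. Or, if secondary status was agreed with FDA, name the variable and its analysis in Protocol 8.5.3 and SAP 6.3.

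**Cost.** The grade needs a change of SAP wording and one recode. The status needs a documented SAP revision and a protocol amendment or administrative change under Protocol 12.1, with any FDA agreement confirmed first. No data collection or sample size changes. The downside is that any summary of the grade would show fewer subjects as improved than the literal rule does, and if the endpoints are exploratory, no lesion result can be presented as key secondary.
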